7.1.3.12 Metabolic syndrome (APP III) Definition

A subject will be deemed as meeting the definition of metabolic syndrome if they meet 3 out of 5 the below criteria at the same visit:

- Waist Circumference >102cm (>40inches)
- Triglycerides > 150mg/dl (>1.69 mmol/L)
- HDL Cholesterol <40mg/dl (<1.036 mmol/L)
- Blood pressure >130mmHg (systolic) or >85mmHg (diastolic)
- Glucose >110 mg/dl (>6.11 mmol/L)

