9.1.2 Schedule of Assessments

The schedule of assessments is presented in [Table 9-1](#).

Table 9–1 Schedule of Assessments

Visit	Screening Phase		Randomisation Phase (Treatment Period)								Follow-Up ¹		
	Screening (D -28 to D -1)		1 (Baseline)	2	3	4	5	6	7	8 (EOT)	9	10	11 (FU)
Week/Day	Screen Visit 1	Screen Visit 2 (Visit 1 + 3-7 days)	D 1	D 8 (±1 D)	W4 (±2 D)	W8 (±2 D)	W12 (±2 D)	W16 (±2D)	W20 (±2 D)	W24 (±2 D)	W28 ² (±2 D)	W32 ² (±2 D)	W36 (±2 D)
Written informed consent	X												
Demographics	X												
Medical/surgical history	X												
Inclusion/exclusion criteria	X												
Androgen deficiency symptom checklist	X												
Randomisation			X										
Full general physical exam and prostate exam and breast exam	X						X			X			
Limited physical exam³			X	X	X	X		X	X				X
Vital signs ⁴ ; height (Visit 1 only)	X		X	X	X	X	X	X	X	X			X
12-Lead ECG	X		X		X	X	X			X			
Specialised chemistry: morning cortisol, TSH, FT4, prolactin, iron, transferrin ⁵	X												
25 hydroxy vitamin D			X										
Clinical laboratory tests: haematology, blood chemistry, eGFR by Cockcroft-Gault formula, dipstick urinalysis ⁶ and PSA ⁷	X		X	X	X	X	X	X	X	X			X
Cardiometabolic parameters 1: HbA1c, fasting lipids (total cholesterol, LDL, HDL, triglycerides) ⁷	X				X		X			X			X
Cardiometabolic parameters 2: Fasting glucose and insulin, hs-CRP, HOMA-IR Bone turnover markers^{7,8}			X				X			X			X
Sex hormones 1: testosterone (total), oestradiol (total), LH	X ^{9, 11}	X ^{9,10, 11}	X ¹¹	X ¹¹	X ¹¹	X ¹¹	X ¹¹	X ¹¹	X ¹¹	X ¹¹			X
Bioavailable testosterone, SHBG			X ¹¹	X ¹¹	X ¹¹	X ¹¹	X ¹¹	X ¹¹	X ¹¹	X ¹¹			X
Sex hormones 2: FSH			X	X	X	X	X	X	X	X			X
DHT, inhibin A and B			X				X			X			X
Semen quality analysis ¹²			X				X		X				
Semen PK samples ¹³										X			
Plasma PK samples ¹⁴							X			X			
Hip and waist measurement			X				X			X			

Visit	Screening Phase		Randomisation Phase (Treatment Period)								Follow-Up ¹		
	Screening (D -28 to D -1)		1 (Baseline)	2	3	4	5	6	7	8 (EOT)	9	10	11 (FU)
Week/Day	Screen Visit 1	Screen Visit 2 (Visit 1 + 3-7 days)	D 1	D 8 (±1 D)	W4 (±2 D)	W8 (±2 D)	W12 (±2 D)	W16 (±2D)	W20 (±2 D)	W24 (±2 D)	W28 ² (±2 D)	W32 ² (±2 D)	W36 (±2 D)
Body composition using bioimpedance ¹⁵ (by impedance)			X				X			X			
Actigraphy ¹⁶			X				X			X			X
Grip strength			X		X	X	X			X			X
PROs: IIEF, BFI, PROMIS SexFS, PROMIS Fatigue Short Form, PGI-S		X ¹⁷	X		X	X	X			X			X
PROs: SF-36			X				X			X			X
DEXA	X ¹⁸									X ¹⁸			

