12.3.1 Clinical Laboratory Tests

Blood Chemistry

Sodium, potassium, chloride, bicarbonate/CO₂, blood urea nitrogen, creatinine, fasting glucose, albumin, alkaline phosphatase, AST, ALT, PT/INR, total bilirubin, total protein, calcium, lipid panel (total cholesterol, LDL, HDL, triglycerides) and PSA will be measured.

eGFR will be calculated based on Cockcroft-Gault formula:

$$\text{eGFR} = ((140 - \text{Age}) / (\text{SerumCreat})) * (\text{Weight} / 72)$$

Haematology

Haemoglobin, white blood cell (WBC) count with differentials (monocytes, eosinophils, basophils, neutrophils, lymphocytes) as an absolute value, red blood cell (RBC) count and platelet count will be measured.

Urinalysis

Specific gravity, pH, semi-quantitative “dipstick” evaluation of glucose, protein, bilirubin, ketones, leukocytes and blood will be measured.

A microscopic examination including RBC and WBC will be performed only when dipstick evaluation is positive for WBC and/or blood or protein. A midstream urine sample (about 30 mL) will be obtained, in order to avoid contamination with epithelial cells and sediments, and allow proper assessments.

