8.1.3 Descriptive statistics

Continuous variables will be summarised using descriptive statistics including number of non-missing observations (n), arithmetic mean (Mean), median (Median), standard deviation (SD), minimum value (Min), maximum value (Max) and number of missing observations (if any). One additional decimal point for mean and median and 2 additional decimal points for SD will be used.

For categorical variables, summaries will include the number of non-missing observations (n) or the number of patients in the population (N) as applicable, the counts of subjects and percentages. Percentages will be rounded to one decimal place. The number of missing values will be presented as a separate category with no percentage, but only if any missing value is recorded in the data for that summary.

Summary statistics will only be presented at each visit for which the parameter is scheduled to be collected.

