8.6.4.3 Changes in Cardiometabolic Disease Markers

Descriptive summary tables will be presented for blood pressure (systolic and diastolic blood pressure), fasting lipid profile (total cholesterol, low density lipoprotein [LDL], triglycerides and HDL), HbA1c, fasting glucose, fasting insulin, high sensitivity C reactive protein (hs CRP) and HOMA-IR values and change from baseline values by treatment regimen and visit.

The change from baseline in each parameter up to Week 24 will be analysed via MMRM in the same manner as the change from baseline in total testosterone (see Section 8.6.3.1).

Non-fasting values of all lipid profile parameters, glucose and insulin will be excluded from both the descriptive summary and analysis.

In addition the number and proportion of subjects who met the definition of metabolic syndrome will be summarised by treatment regimen at each visit (baseline and post-baseline).

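### Metabolic syndrome is scored as 3 of 5 criteria at one visit and tabulated at each visit, but waist is measured at only three visits, so apparent prevalence falls at the others

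*SAP*

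**What the plan says.** Under SAP 7.1.3.12 each man "will be deemed as meeting the definition of metabolic syndrome if they meet 3 out of 5 the below criteria at the same visit". The five criteria are waist, triglycerides, HDL cholesterol, blood pressure and glucose. The section has no rule for a criterion that was not measured.

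SAP 8.6.4.3 asks for counts and percentages of men who "met the definition of metabolic syndrome will be summarised by treatment regimen at each visit (baseline and post-baseline"). It also excludes non-fasting lipid and glucose values from the summaries and analyses of that section.

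In Protocol Table 9-1 (section 9.1.2), the row "Hip and waist measurement" is marked at Baseline, Week 12 and Week 24 only. Blood pressure, as a vital sign, is marked at every clinic visit.

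Lipids appear twice. The row "Cardiometabolic parameters 1: HbA1c, fasting lipids (total cholesterol, LDL, HDL, triglycerides") is marked at Screening and Weeks 4, 12, 24 and 36. The row "Clinical laboratory tests: haematology, blood chemistry, eGFR by Cockcroft-Gault formula, dipstick urinalysis" is marked at Screening, Baseline, every treatment visit and Week 36. Protocol 12.3.1 lists fasting glucose in the blood chemistry and adds that the "lipid panel (total cholesterol, LDL, HDL, triglycerides) and PSA will be measured". SAP 8.7.2.1 repeats both the panel and the timing.

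SAP 8.1.3 sets a general limit: "Summary statistics will only be presented at each visit for which the parameter is scheduled to be collected". SAP 7.2.1 says summary tables use observed cases without imputation unless otherwise specified.

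**The concern.** A count of criteria against a fixed threshold is comparable over time only if the same criteria can be counted each time. Here one of the five is absent by design at six of the nine clinic visits from Baseline on, and the threshold does not move.

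The absent criterion is probably the one most often met. Every man enters with BMI above 30 kg/m², so a waist above 102 cm should be common. That is an inference, since the documents give no waist data. For a man with a large waist, the working requirement changes from two of the other four criteria to three of the other four.

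At stake is the reading of one exploratory table. Followed to the letter, it would show metabolic syndrome falling after Baseline, returning at Week 12, falling again and returning at Week 24, in placebo and active arms alike. The primary endpoint, type I error and power are not involved.

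**Working it through.** The plan states no prevalence of metabolic syndrome, so there is no figure to reproduce. The check has two parts.

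**1. Criteria scheduled at each visit** (Protocol Table 9-1 and 12.3.1; SAP 8.7.2.1 and 8.7.3)

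| Visit | Waist | Triglycerides and HDL (chemistry) | Blood pressure | Glucose (chemistry) | Criteria |
|---|---|---|---|---|---|
| Baseline, Week 12, Week 24 | yes | yes | yes | yes | 5 of 5 |
| Day 8, Weeks 4, 8, 16, 20, 36 | no | yes | yes | yes | 4 of 5 |

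Weeks 28 and 32 are telephone contacts.

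**2. Size of the artefact**

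Let w be the proportion meeting the waist criterion, and let N be the number met among the other four. With independence between waist and the rest:

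- waist measured: prevalence = w × P(N ≥ 2) + (1 − w) × P(N ≥ 3)
- waist not measured and scored as not met: prevalence = P(N ≥ 3)
- difference = w × P(N = 2)

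Without independence, the difference is the proportion of men who meet waist and exactly two others. It is therefore never negative, and only its size depends on the assumptions.

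The inputs below are assumptions, not document figures: w = 97%, with three sets of prevalences for triglycerides, HDL, blood pressure and glucose, all independent.

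| Assumed prevalences | P(N ≥ 2) | P(N ≥ 3) | Waist measured | Waist not measured |
|---|---|---|---|---|
| 30, 30, 40, 20% | 0.3476 | 0.0804 | 0.97 × 0.3476 + 0.03 × 0.0804 = 34% | 8% |
| 50, 40, 50, 35% | 0.5900 | 0.2225 | 0.97 × 0.5900 + 0.03 × 0.2225 = 58% | 22% |
| 60, 50, 65, 50% | 0.7775 | 0.4100 | 0.97 × 0.7775 + 0.03 × 0.4100 = 77% | 41% |

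For the first row, P(N = 0) = 0.7 × 0.7 × 0.6 × 0.8 = 0.2352 and P(N = 1) = 0.4172, so P(N ≥ 2) = 1 − 0.2352 − 0.4172 = 0.3476.

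A wider grid (w from 85% to 100%, the other four equal at 30% to 60%) gives 31% to 82% with waist and 8% to 48% without. The drop is about 22 to 38 percentage points.

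**Would a missing-component rule be enough without restricting visits?** No. Without waist, a man with exactly two of four met cannot be classified. In the three sets that is 0.3476 − 0.0804 = 27%, 0.5900 − 0.2225 = 37% and 0.7775 − 0.4100 = 37% of men. Among the rest, prevalence would be 0.0804/0.7328 = 11%, 0.2225/0.6325 = 35% and 0.4100/0.6325 = 65%, still not the five-criterion values.

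**The case against.** **SAP 8.1.3 already settles it.** A natural reading is that a composite is shown only where its components are scheduled, which would leave Baseline, Week 12 and Week 24. This is a fair reading and may be the intended one, and the table shells, which are in a separate document, may say so. But the composite has no schedule row of its own, four of its five components are scheduled at the other visits, and 8.6.4.3 says each visit. Two programmers could produce different tables from the same text.

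**The observed-case rule in SAP 7.2.1 forbids scoring an unmeasured waist as not met.** It does sit badly with that scoring. But it does not say whether a man with two criteria met and waist unmeasured counts as not met or as missing. The SAP gives such rules for other derived scores (IIEF, PROMIS Fatigue, BFI in 7.1.3.3, 7.1.3.5 and 7.1.3.6), but not for this one.

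**The item is minor.** This stands. Metabolic syndrome is not among the endpoints listed in SAP section 4, and no test is planned for it. Because all arms follow one schedule, a missing waist cannot by itself create a difference between arms.

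**A stronger reading that the documents do not support.** From the blank Baseline cell in the lipid row of Table 9-1, a reader might infer that only three criteria exist at Baseline, and that prevalence would therefore rise from Baseline to Week 24 in every arm. The blood chemistry panel includes the lipid panel and fasting glucose and is drawn at Baseline (Protocol 12.3.1, SAP 8.7.2.1), and Protocol 12.3 requires all blood samples to be fasting. SAP 8.1.5 would in any case accept the last pre-dose value as baseline. The comparison of Baseline with Weeks 12 and 24 has no schedule artefact.

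**Conclusion.** The point holds for waist only. Read literally, SAP 7.1.3.12 and 8.6.4.3 apply a threshold of three to four measurable criteria at Day 8 and Weeks 4, 8, 16, 20 and 36, and apparent prevalence falls there without any change in the men. The illustrated fall is 26 to 36 percentage points in the three main sets (34% to 8%, 58% to 22%, 77% to 41%). These sizes rest on assumed prevalences, on independence, and on scoring an unmeasured waist as not met. Correlation between components was not examined and would change them.

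The distortion affects the time course within arms. It gives no ground for expecting a spurious difference between arms, nor for doubting the comparability of Baseline, Week 12 and Week 24.

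A smaller gap remains at those three visits. If the exclusion of non-fasting values in 8.6.4.3 carries over to the composite, a man with a non-fasting sample loses triglycerides, HDL and glucose. He then has only two observable criteria, so he can never reach three, and the SAP does not say how to class him.

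Severity is minor: this is a descriptive count in an exploratory section.

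**What to change.** Amend SAP 7.1.3.12 and 8.6.4.3 as follows.

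1. Tabulate metabolic syndrome only at Baseline, Week 12 and Week 24.
2. State that triglycerides, HDL and glucose come from the fasting blood chemistry panel. For the baseline classification, use each component's last pre-dose value under SAP 8.1.5 in place of the same-visit condition.
3. Class a man as met if at least three observed criteria are met, and as not met if fewer than three could be met even if every missing criterion counted as met. Otherwise class him as missing and leave him out of the denominator. Show the number missing by arm and visit.

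Step 1 removes the waist artefact. Step 3 deals with individual men who lack a waist or a fasting value at the retained visits.

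The cost is a few SAP sentences and no new data. The table loses six visits at which the composite cannot be fully assessed, and some men will be unclassified.

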7.1.4 Definitions relative to safety parameters

7.1.4.1 Adverse Event (AE)

Treatment Emergent Adverse Event (TEAE)

A Treatment Emergent AE (TEAE) is defined as an AE occurring or worsening on or after the first dose of study medication. For subjects that enter the extension study, only AE's occurring prior to entering the extension study will be considered a TEAE and summarised.

TEAEs will also be split between AEs that start during the treatment period and those that start on or after the first day of the follow-up period (for subjects not entering the extension study).

Duration of AEs

The duration of an AE will be calculated as the resolution date minus the start date plus 1.

7.1.4.2 Treatment Compliance

Duration of Exposure

The duration of Exposure to study medication (number of days) will be defined as:

(date of last dose of study medication – date of first dose of study medication) + 1

Treatment Compliance

Overall treatment compliance will be defined as:

$$\frac{100\% \times [\text{Total Number of capsules dispensed} - \text{Total Number of capsules returned}]}{[(\text{Duration of Exposure (weeks)} \times \text{Number of capsules expected to be taken (3)})]}$$

Where Duration of Exposure (weeks) = [duration of exposure (days) / 7] rounded up to the nearest integer to derive the number of weeks started medication.

If either the duration of exposure is missing or the number of (Number of capsules dispensed – Number of capsules returned) cannot be calculated then the compliance calculation will not be computed.

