Due to the potential for dehydration to affect Haematocrit, subjects should be fully hydrated at the time of screening and during the trial when the haematocrit is tested, to ensure a reliable result both for study eligibility assessment and the ongoing monitoring (with respect to the haematocrit stopping criterion).

Eligible subjects will be randomised on Day 1 (Baseline) in a 1:1:1:1 ratio to one of the following treatment groups, consisting of three capsules per dose taken weekly:

-
-
-

Once approximately 100 of the overall planned enrolled subjects have completed the Week 4 visit, an interim analysis will be performed by an independent DMC who will review unblinded data and determine whether the criteria for normalisation of testosterone (testosterone within or above normal reference range for healthy adult males according to FDA criteria) were met. The DMC will establish whether an individual arm has met the criteria of $\geq 75\%$ of subjects reaching the normalisation of testosterone, or whether in the opinion of the DMC following unblinded review that when the arm is fully recruited it is expected to achieve a $\geq 75\%$ response at Week 24 (see [Section 13.6](#)). Dosing arms which meet either of these criteria will be deemed effective. For dosing arms deemed to be ineffective, dosing will be stopped and no further randomisation to that arm will be performed. Subjects assigned to ineffective or unsafe arm(s), as determined per the DMC, will be discontinued from the study, will attend Visit 8 (EOT) and will be followed-up for an additional 12 weeks (FU, Visit 11) and will not be eligible for MBGS206 extension study. Recruitment will continue while the interim analysis is ongoing.

The remainder of the randomisation will then continue in a 1:1:1 ratio of remaining active arms versus placebo to the following treatment groups:

During the 24-week treatment period, subjects in the BGS649 groups and the matching placebo group will take the required dose weekly (± 1 day from the time schedule of regular planned dose). The treatment period consists of 24 weekly doses providing therapeutic coverage to week 24 due to long half-life of BGS649. The capsule will be taken orally by the subject with water.

Seminal Fluid Evaluation:

Semen Quality

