- Discontinue investigational treatment for a subject if individual serum creatinine increases $\geq 50\%$ compared to Baseline (and is considered clinically significant), or in the event of treatment emergent proteinuria (albumin:creatinine ratio [ACR] >300 mg/g or >30 mg/mmol; protein:creatinine ratio [PCR] ≥ 500 mg/g or >50 mg/mmol). (Creatinine can be repeated once within 7 days of initial alert. Study drug administration should be suspended during this time and resumed only if repeat creatinine is back to pre-alert level)
 - A renal event leading to subject discontinuation should be followed up until event resolution (serum creatinine within 10% of Baseline, protein-creatinine ratio within 50% of Baseline), stabilises or becomes not clinically significant, or is assessed as being chronic.
6. Subject missed 4 or more consecutive study drug dosing.
 7. Development of prostate cancer or PSA increase more than 1.4 ng/ml above Screening level. It is recommended that in these cases subjects undergo urologic consultation.
 8. Haematocrit $>54\%$ (Hematocrit can be repeated once within 7 days of initial alert. Study drug administration should be suspended during this time and resumed only if repeat hematocrit is under 54%)
 9. Development of sleep apnoea.
 10. Development of cardiovascular event (significant arrhythmia acute myocardial infarction, brain stroke, transient ischemic attack, unstable angina, congestive heart failure).
 11. Emergence of the following adverse events:
 - Absolute QTcF >500 msec, or a rise of QTcF of ≥ 60 msec above baseline confirmed by triplicate ECG measurements.
 12. Pregnancy in female sexual partner of the male study subject, occurring after the start of study treatment.
 13. Fragility bone fracture.
 14. Breast cancer.

Procedures for handling patients incorrectly enrolled or randomized

Subjects who fail to meet the inclusion/exclusion criteria must not be enrolled or randomized. If a subject not meeting the study criteria is randomized in error, a discussion must occur between the Medical Monitor and the investigator regarding whether to continue or discontinue the subject from the study. If agreement is reached, the subject should complete the study unless there are safety concerns or if the subject withdraws the consent.

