6.3 Per-Protocol population (PP)

The PP population is a subset of the ITT population and includes all randomised subjects who have been treated according to the protocol and fulfil the following criteria (to be further described in the classification meeting plan):

1. Specific inclusion/exclusion criteria satisfied
2. Absence of relevant protocol violations with respect to factors likely to affect the efficacy of treatment where the nature of protocol violation will be defined before breaking the blind
3. Adequate study medication compliance
4. Adequate measurement of the primary variable.

Subjects will be analysed according to the treatment to which they were randomised.

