8.5.2 Treatment compliance

The overall treatment compliance (in %) will be presented by treatment regimen using the Safety population. The number of subjects with overall compliance <80% or >120% will be presented

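### Overall compliance is divided by the weeks up to the last dose taken, so doses due but missed after that dose cannot lower the score

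*SAP*

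**What the plan says.** SAP 7.1.4.2 builds the measure in three steps.

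- Duration of exposure in days is ("date of last dose of study medication – date of first dose of study medication) + 1".
- That duration is divided by 7 and "rounded up to the nearest integer to derive the number of weeks started medication".
- Compliance is 100% times ("Total Number of capsules dispensed" minus the total returned), divided by weeks of exposure times the "Number of capsules expected to be taken (3").

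SAP 8.5.2 reports the result for the Safety population: "The number of subjects with overall compliance <80% or >120% will be presented". SAP 6.3 lists "Adequate study medication compliance" among the per-protocol (PP) criteria. It gives no numeric threshold and leaves the detail to a classification meeting plan.

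On dosing, Protocol 9.1.1 states: "The treatment period consists of 24 weekly doses". Among the grounds on which treatment must be permanently discontinued, Protocol 9.3.7 lists: "Subject missed 4 or more consecutive study drug dosing".

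**The concern.** The denominator stops at the last dose actually swallowed. No passage extends it to the decision to stop treatment, to Visit 8 or to the 24 planned doses. A run of missed doses at the end therefore drops out of the expected intake, while the same run in mid-course counts in full. The measure is most generous to men whose adherence lapsed at the end, including those stopped under the four-missed-doses rule.

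Two uses are at stake. The first is the count of men below 80% in SAP 8.5.2, which is meant to show how many took too little drug. The second is the PP set, which supports the primary endpoint (SAP 8.6.2) and is the population for the Week 24 association analyses (SAP 8.8.4). Adequate compliance is one of its entry criteria.

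**Working it through.** **Inputs.** The formula and the three capsules per dose come from SAP 7.1.4.2, the 24 weekly doses from Protocol 9.1.1, the four-missed-doses rule from Protocol 9.3.7 and the 80% and 120% limits from SAP 8.5.2. I assume dosing on Days 1, 8, 15 and so on, so dose k falls on Day 7(k − 1) + 1. The documents give no worked compliance figure to reproduce.

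**Formula.** Compliance = 100 × (capsules dispensed − returned) / (3 × weeks), where weeks = (last dose day − first dose day + 1)/7, rounded up.

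**Full complier.** Dose 24 falls on Day 162. 162/7 = 23.1, rounded up to 24 weeks. Compliance is 72/72 = 100%, so the formula works for a full course.

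**Stopped after four consecutive missed doses.** He takes doses 1 to 10, misses 11 to 14 and is discontinued from treatment. Dose 10 falls on Day 64, and 64/7 = 9.1, rounded up to 10 weeks.

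- Unused capsules returned: 30/30 = 100%. Against the 14 doses due he took 30/42 = 71.4%.
- The 12 capsules for doses 11 to 14 not returned: 42/30 = 140%.
- One more dose taken in week 15 before he is stopped: Day 99, and 99/7 = 14.1, rounded up to 15 weeks, so 33/45 = 73.3%. Here the gap does count.

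**Completer who misses the last three doses.** His last dose is dose 21 on Day 141. 141/7 = 20.1, rounded up to 21 weeks, so 63 capsules are expected instead of 72. He also misses two to four earlier doses that do not form a run of four, and returns the unused capsules.

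| Earlier doses missed | Doses taken | Share of 24 doses | SAP score |
|---|---|---|---|
| 2 | 19 | 57/72 = 79.2% | 57/63 = 90.5% |
| 3 | 18 | 54/72 = 75.0% | 54/63 = 85.7% |
| 4 | 17 | 51/72 = 70.8% | 51/63 = 81.0% |

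All three took less than 80% of the course, and none is flagged.

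**Position alone changes the score.** Three consecutive doses missed at weeks 9 to 11, with dosing resumed to week 24, give 63/72 = 87.5%. The same three missed as the last of 24 give 63/63 = 100%. For four doses the figures are 60/72 = 83.3% and 60/60 = 100%, although the discontinuation rule should prevent resumption after a mid-course gap of four.

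**A side effect of the rounding.** If dose 12 is taken one day early, within the permitted ±1 day, exposure is 77 days or exactly 11 weeks, and a man who missed nothing scores 36/33 = 109.1%.

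**The case against.** The strongest reply is that this is a definition and not an error. The formula measures intake while on drug and gives a full complier 100%. Early stopping is reported elsewhere, through treatment duration (SAP 8.5.1) and reasons for treatment discontinuation (SAP 8.2). That holds for men who stop early, who will be visible in those tables. It does not cover the completers in the table above, whose low intake the <80% count should show. The SAP also calls the measure overall compliance and does not restrict it to time on drug.

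The reply is stronger on consequences. A reader might infer that men stopped for missed doses would be kept in the PP set and distort the supportive analysis. The documents do not support that. No passage ties the 80% limit to PP membership. SAP 6.6 has exclusions settled at a classification meeting before unblinding, from eCRF listings, deviation logs and other sources. SAP 6.3 has separate criteria for relevant violations and adequate measurement of the primary variable.

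A reader might also infer that every man stopped under the rule scores 100%. That needs no earlier miss, no dose after the gap and all unused capsules returned. With the capsules unreturned, the man in the example scores 140% and the >120% limit catches him.

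Finally, no loss of efficacy can be claimed from doses missed just before Week 24. Protocol 9.2 gives a half-life of 21 days, and Protocol 9.1.1 relies on it for coverage to Week 24.

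**Conclusion.** The point holds as a minor defect in a derived variable. Doses due but missed after the last one taken cannot lower the score. The result can be 100% for a man who took 71.4% of the doses due, and 81.0% to 90.5% for completers who took 70.8% to 79.2% of the course. The <80% count in SAP 8.5.2 misses these men.

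The figures assume weekly dosing on schedule and return of all unused capsules. The completer cases also need two to four earlier misses: the last three doses alone leave 21/24 = 87.5%, which is unflagged on either definition. The primary ITT analysis does not use compliance and is unaffected. Any effect on the PP set cannot be quantified from the documents.

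**What to change.** In SAP 7.1.4.2, replace weeks of exposure in the denominator with the number of weekly doses due from the first dose to the earlier of Visit 8 and the date of the decision to discontinue treatment, times three capsules. Three details belong in the text:

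- The end date is the date of the decision, explicitly not the date of the last dose; otherwise the defect returns.
- The count is 24 doses for completers.
- Doses withheld during a protocol-required suspension (the repeat liver, creatinine and haematocrit tests in Protocol 9.3.7) are left out.

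The man who took 10 of 14 doses then scores 30/42 = 71.4%, and the completers score 79.2%, 75.0% and 70.8%; all are flagged. A man who takes 16 doses and then misses four scores 48/60 = 80.0% and is still not flagged. Counting doses due also removes the 109.1% artefact.

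The change does not cure unreturned capsules, which the numerator still counts as taken: the man at 140% would score 42/42 = 100% and lose his >120% flag. The intake dates entered in the EDC (Protocol 10.4) are the cross-check for that.

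The cost is one line in the SAP and its derivation, and some compliance values become lower. Treatment duration and discontinuation reasons continue to report early stopping separately.
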